6.8. Appendix 8 Adverse Events of Special Interest

Adverse events of special interest list of MedDRA preferred terms.

Adverse Event of Special Interest	Source	Preferred Term
ALT/AST elevation	(Modified) Liver related investigations, signs and symptoms (SMQ) narrow, (MedDRA v25.1)	Alanine aminotransferase abnormal Alanine aminotransferase increased Aspartate aminotransferase abnormal Aspartate aminotransferase increased Hepatic enzyme abnormal Hepatic enzyme increased Hepatic function abnormal Hypertransaminasaemia Liver function test abnormal Liver function test increased Transaminases abnormal Transaminases increased
Renal Complications	(Modified) Acute renal failure (SMQ) broad (MedDRAv25.1)	Acute kidney injury Anuria Nephropathy toxic Oliguria Renal failure Renal impairment Subacute kidney injury Blood creatinine abnormal Blood creatinine increased Creatinine renal clearance abnormal Creatinine renal clearance decreased Creatinine urine abnormal Creatinine urine decreased Crystal nephropathy Glomerular filtration rate abnormal Glomerular filtration rate decreased Nephritis Proteinuria Renal function test abnormal Renal tubular disorder Renal tubular dysfunction

Adverse Event of Special Interest	Source	Preferred Term
		Renal tubular injury
		Renal tubular necrosis
		Urine output decreased
		Nephropathy
		Nephropathy toxic
		Glomerulonephropathy
		Nephrolithiasis
Cholesterol increase	Dyslipidaemia (SMQ), (MedDRA v25.1)	Blood cholesterol abnormal
		Blood cholesterol esterase increased
		Blood cholesterol increased
		Dyslipidaemia
		High density lipoprotein abnormal
		High density lipoprotein decreased
		High density lipoprotein increased
		Hypercholesterolaemia
		Hyperlipidaemia
		Hypo HDL cholesterolaemia
		Intermediate density lipoprotein decreased
		Intermediate density lipoprotein increased
		LDL/HDL ratio decreased
		LDL/HDL ratio increased
		Lipid metabolism disorder
		Lipids abnormal
		Lipids increased
		Lipoprotein abnormal
		Lipoprotein increased
		Low density lipoprotein abnormal
		Low density lipoprotein decreased
		Low density lipoprotein increased
		Non-high-density lipoprotein cholesterol decreased
		Non-high-density lipoprotein cholesterol increased
		Primary hypercholesterolaemia
		Remnant hyperlipidaemia
		Remnant-like lipoprotein particles increased
		Total cholesterol/HDL ratio abnormal
		Total cholesterol/HDL ratio decreased
		Total cholesterol/HDL ratio increased
		Very low density lipoprotein abnormal

Adverse Event of Special Interest	Source	Preferred Term
		Very low density lipoprotein decreased Very low density lipoprotein increased
Hematologic abnormalities	(Modified) Haematopoietic cytopenias affecting more than one type of blood cell (SMQ), (MedDRA v25.1)	Aplastic anaemia Autoimmune aplastic anaemia Bicytopenia Bone marrow failure Cytopenia Febrile bone marrow aplasia Full blood count decreased Gelatinous transformation of the bone marrow Immune-mediated pancytopenia Pancytopenia Panmyelopathy Aspiration bone marrow abnormal Biopsy bone marrow abnormal Full blood count abnormal Blood disorder Bone marrow disorder Bone marrow infiltration Bone marrow myelogram abnormal Bone marrow necrosis Haematotoxicity Myelodysplastic syndrome Myelodysplastic syndrome transformation Myelofibrosis Myeloid metaplasia Plasmablast count decreased Scan bone marrow abnormal
	(Modified) Haematopoietic erythropenia (SMQ), (MedDRA v25.1)	Aplasia pure red cell Aplastic anaemia Erythroblast count decreased Erythroid maturation arrest Erythropenia Hypoplastic anaemia Microcytic anaemia

Adverse Event of Special Interest	Source	Preferred Term
		Proerythroblast count decreased
		Red blood cell count decreased
		Reticulocyte count decreased
		Reticulocytopenia
		Anaemia
		Erythroblast count abnormal
		Erythropoiesis abnormal
		Haematocrit abnormal
		Haematocrit decreased
		Haemoglobin abnormal
		Haemoglobin decreased
		Leukoerythroblastic anaemia
		Normochromic anaemia
		Normochromic normocytic anaemia
		Normocytic anaemia
		Proerythroblast count abnormal
		Red blood cell count abnormal
		Reticulocyte count abnormal
		Reticulocyte percentage decreased
	(Modified) Haematopoietic leukopenia (SMQ), (MedDRA v25.1)	Agranulocytosis
		Band neutrophil count decreased
		Band neutrophil percentage decreased
		Basophil count decreased
		Basophilopenia
		B-lymphocyte count decreased
		Cyclic neutropenia
		Eosinopenia
		Eosinophil count decreased
		Febrile neutropenia
		Granulocyte count decreased
		Granulocytes maturation arrest
		Granulocytopenia
		Idiopathic neutropenia
		Leukopenia
		Lymphocyte count decreased
		Lymphopenia
		Metamyelocyte count decreased
		Monoblast count decreased

Adverse Event of Special Interest	Source	Preferred Term
		Monocyte count decreased
		Monocytopenia
		Myeloblast count decreased
		Myelocyte count decreased
		Neutropenia
		Neutropenic infection
		Neutropenic sepsis
		Neutrophil count decreased
		Promyelocyte count decreased
		Pure white cell aplasia
		T-lymphocyte count decreased
		White blood cell count decreased
		Basophil count abnormal
		Basophil percentage decreased
		B-lymphocyte abnormalities
		B-lymphocyte count abnormal
		Differential white blood cell count abnormal
		Eosinophil count abnormal
		Eosinophil percentage decreased
		Full blood count abnormal
		Granulocytes abnormal
		Leukopenia neonatal
		Lymphocyte count abnormal
		Lymphocyte percentage abnormal
		Lymphocyte percentage decreased
		Monocyte count abnormal
		Monocyte percentage decreased
		Mononuclear cell count decreased
		Myeloblast percentage decreased
		Myelocyte percentage decreased
		Myeloid maturation arrest
		Neutrophil count abnormal
		Neutrophil percentage decreased
		Plasma cell disorder
		Plasma cells absent
		White blood cell analysis abnormal
		White blood cell count abnormal
		White blood cell disorder

Adverse Event of Special Interest	Source	Preferred Term
	(Modified) Haematopoietic thrombocytopenia (SMQ), (MedDRA v25.1)	Acquired amegakaryocytic thrombocytopenia Megakaryocytes decreased Platelet count decreased Platelet maturation arrest Platelet production decreased Platelet toxicity Thrombocytopenia Megakaryocytes abnormal Platelet count abnormal Platelet disorder Plateletcrit abnormal Plateletcrit decreased

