2.3.2.2.2. Potential Risks for JNJ-6379

Since the initial protocol writing, interim results of the REEF-1 and REEF-2 studies had become available. The data suggested that JNJ-6379 has a negative impact on the HBsAg lowering effect of JNJ-3989+NA (see Section 2.2.3.1). In addition, there were new insights in the adverse renal profile of JNJ-6379, resulting from increase in biomarkers of proximal renal tubular injury observed in REEF-2. Taken together, it was concluded that JNJ-6379 had an unfavorable benefit-risk balance in combination with JNJ-3989+NA, compared to JNJ-3989+NA alone. Therefore, the

Sponsor decided to discontinue treatment with JNJ-6379 in all ongoing clinical studies effective immediately. For completeness, the potential risks for JNJ-6379 are still described in this section.

Reproductive Risks and Pregnancy

In the fertility study in females, early embryonic development was affected: an increase in pre- and post-implantation loss, reduction in implantation and live fetuses at 300 mg eq./kg/day. The fetal loss seen during the early stages of pregnancy was considered the result of low hormone levels (decreased luteinizing hormone, progesterone, estradiol) induced by treatment with JNJ-6379.

In the EFD studies, JNJ-6379 was not teratogenic in rats and rabbits.

In the EFD study in rats, fetal weights at 300 mg eq./kg/day were lowered, and there was retarded ossification from 100 mg eq./kg/day onwards. The NOAEL for EFD was considered to be **CC** mg eq./kg/day. At this dose, the AUC_{0-24h} was 84,000 ng.h/mL and the C_{max} was 5,190 ng/mL.

In the EFD study in rabbits, the NOAEL for EFD was considered to be the highest dose tested, ie, **CC** mg eq./kg/day. At this dose, the AUC_{0-24h} was 99,200 ng.h/mL and the C_{max} was 6,880 ng/mL.

Potential Genotoxicity

JNJ-6379 was not genotoxic in the in vitro and in vivo tests.

JNJ-6379 did not affect male or female fertility. Carcinogenicity studies are not yet conducted.

Other Potential Toxicity/Events of Special Interest

Based on nonclinical findings in rats and dogs and based on clinical findings, increased cholesterol was identified as a laboratory abnormality of interest.

Viral Resistance

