8.2.4. Clinical Safety Laboratory Assessments

Refer to Section 8.2.4 of the Master Protocol PLATFORMPAHPB2001.

In addition, urine samples for urine chemistry and renal biomarkers will be collected as noted in Section 10.2, Appendix 2: Clinical Laboratory Tests.

For this study, the laboratory abnormality of cholesterol increase is identified as laboratory abnormality of interest.

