8.3.6. Adverse Events of Special Interest

Events of Special Interest are significant AEs that are judged to be of special interest because of clinical importance, known class effects or based on nonclinical signals. Events of Special Interest that will be carefully monitored during the study include ISRs, ALT/AST elevations, renal complications, hematologic abnormalities, and events related to cholesterol increase (Section 8.2.4, Clinical Safety Laboratory Assessments). In addition, the following toxicities will also be carefully monitored: rash and acute systemic allergic reactions.

For participants reporting rash, ISRs, acute systemic allergic reactions, ALT/AST elevations, renal complications, and hematologic abnormalities as specified in the DAIDS Toxicity Grading Scale (see Section 10.9, Appendix 9: DAIDS Table), the following should be done.

Note: renal complications and cholesterol increase are AESIs specific for JNJ-6379, which was part of the study intervention prior to Protocol Amendment 3 and has been removed with the implementation of Protocol Amendment 3. Because most participants who were enrolled before Protocol Amendment 3 was in effect, also received JNJ-6379 as part of their study intervention, the AESIs have not been revised with the removal of JNJ-6379.

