Creatinine Clearance⁹ or eGFR, Low Report only 1^P	NAP	<90 to 60 ml/min or ml/min/1.73 m ² OR 10% to <30% decrease from participant's baseline	<60 to 30 ml/min or ml/min/1.73 m ² OR 30% to <50% decrease from participant's baseline	<30 ml/min or ml/min/1.73 m ² OR ≥50% decrease from participant's baseline or dialysis needed
Glucose (mg/dL; mmol/L) Fasting, High	110 to <125 6.11 to <6.95	125 to <250 6.95 to <13.89	250 to <500 13.89 to <27.75	≥500 ≥27.75
Nonfasting, High	116 to <160 6.44 to <8.89	160 to <250 8.89 to <13.89	250 to <500 13.89 to <27.75	≥500 ≥27.75
Glucose, Low (mg/dL; mmol/L) aged ≥1 month	55 to 64 3.05 to <3.55	40 to <55 2.22 to <3.05	30 to <40 1.67 to <2.22	<30 <1.67
aged <1 month	50 to 54 2.78 to <3.00	40 to <50 2.22 to <2.78	30 to <40 1.67 to <2.22	<30 <1.67
Lactate, High	ULN to <2.0×ULN without acidosis	≥2.0×ULN without acidosis	Increased lactate with pH <7.3 without life-threatening consequences	Increased lactate with pH <7.3 with life-threatening consequences

eGFR: estimated glomerular filtration rate; LLN: lower limit of normal; NAP: not applicable; ULN: upper limit of normal

^P Reminder: Choose the method that selects for the higher grade.

⁹ Use the applicable formula (ie, Cockcroft-Gault in mL/min or Schwartz, modification of diet in renal disease study [MDRD], or Chronic Kidney Disease Epidemiology Collaboration [CKD-EPI] in mL/min/1.73m²). Sites should choose the method defined in their study and when not specified, use the method most relevant to the study population.

LABORATORY VALUES				
CHEMISTRIES				
PARAMETER	GRADE 1 MILD	GRADE 2 MODERATE	GRADE 3 SEVERE	GRADE 4 POTENTIALLY LIFE- THREATENING
Lipase, High	1.1 to <1.5×ULN	1.5 to <3.0×ULN	3.0 to <5.0×ULN	≥5.0×ULN
Lipid Disorders (mg/dL; mmol/L) Cholesterol, Fasting, High aged ≥18 years	200 to <240 5.18 to <6.19	240 to <300 6.19 to <7.77	≥300 ≥7.77	NAP
aged <18 years	170 to <200 4.40 to <5.15	200 to <300 5.15 to <7.77	≥300 ≥7.77	NAP
LDL, Fasting, High aged ≥18 years	130 to <160 3.37 to <4.12	160 to <190 4.12 to <4.90	≥190 ≥4.90	NAP
aged >2 to <18 years	110 to <130 2.85 to <3.34	130 to <190 3.34 to <4.90	≥190 ≥4.90	NAP
Triglycerides, Fasting, High	150 to 300 1.71 to 3.42	>300 to 500 >3.42 to 5.7	>500 to 1,000 >5.7 to 11.4	>1,000 >11.4

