5.6.2. Adverse Events

The verbatim terms used in the CRF by investigators to identify adverse events will be coded using the Medical Dictionary for Regulatory Activities (MedDRA version 21.1 or higher). Any AE occurring at or after the initial administration of study intervention is considered to be treatment emergent. If the event occurs on the day of the initial administration of study intervention, and

either event time or time of administration are missing, then the event will be assumed to be treatment emergent. If the event date is recorded as partial or completely missing, then the event will be considered to be treatment emergent unless it is known to be prior to the first administration of study intervention based on partial onset date or resolution date. All reported treatment-emergent adverse events will be included in the analysis. For each adverse event, the number and percentage of participants who experience at least 1 occurrence of the given event will be summarized.

Summary tables and listings will be provided for treatment-emergent adverse events:

- AEs
- Serious AEs (SAEs)
- AEs leading to discontinuation of any study agent within a study intervention including NA
- AEs by relationship to each study agent within a study intervention including NA

In addition to the summary tables, listings will be provided for participants who experienced any:

- SAEs
- AEs leading to discontinuation of each study agent within a study intervention including NA

For participants reporting rash, a listing with specific grade will be provided.

Incidence of treatment-emergent adverse events of special interest will be summarized by analysis phase and overall.

The adverse events of special interest include:

- ALT/AST elevations
- Injection Site Reactions Related to JNJ-3989
- Renal Complications
- Cholesterol increase
- Hematologic abnormalities (platelet count, hemoglobin, reticulocytes, neutrophil count)

The list of all preferred terms belonging to ALT/AST elevation, renal complication, cholesterol increase, and hematologic abnormalities is provided in [Appendix 8](#). Injection site reactions will be identified using the eCRF Injection Site Reaction form.

A listing of participants who died will be provided.

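### The SAP's preferred-term list for the adverse event of special interest Cholesterol increase includes four terms that denote a fall in a cholesterol-carrying fraction (4 of 33), and two further terms that denote a fall in a cholesterol ratio

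*SAP*

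**What the plan says.** Protocol Section 8.3.6 lists the events of special interest, ending with "hematologic abnormalities, and events related to cholesterol increase". Section 8.2.4 says that "the laboratory abnormality of cholesterol increase is identified as laboratory abnormality of interest". Section 2.3.2.2.2 gives the origin: from findings in animals and in patients given JNJ-6379, "increased cholesterol was identified as a laboratory abnormality of interest". Section 8.3.6 adds that this AESI is specific to JNJ-6379. It was kept after Amendment 3 because most participants enrolled before that amendment had received the drug.

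SAP Section 5.6.2 carries the category forward under the name Cholesterol increase and fixes its content: "The list of all preferred terms belonging to ALT/AST elevation, renal complication, cholesterol increase, and hematologic abnormalities is provided in" Appendix 8. The output is also stated there: "Incidence of treatment-emergent adverse events of special interest will be summarized by analysis phase and overall".

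SAP Appendix 8 fills the category from the Dyslipidaemia SMQ (MedDRA v25.1). Among the terms listed are "Low density lipoprotein decreased" and "Non-high-density lipoprotein cholesterol decreased".

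**The concern.** Label and content disagree. The protocol's event is a rise in cholesterol, while the list that decides who is counted contains both the increased and the decreased form of several lipid terms. Both forms feed the same numerator, and nothing in the SAP limits the category to increases.

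The AESI exists to describe a suspected effect of JNJ-6379, and the counts are likely to be small. Protocol Section 2.2.3.1 reports cholesterol increase as an adverse event in 4 participants (4.1%) in pooled Phase 1 studies, 1 (2.4%) in a further Phase 1 study, and none in the Phase 2a study. Against numbers of that order, a single case in the wrong direction is visible in the table and would be read as evidence for the effect it contradicts.

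**Working it through.** The plan states no figure to reproduce here. The check compares the definition with the list and then counts terms.

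**Step 1: direction in the protocol.** Sections 8.3.6, 8.2.4 and 2.3.2.2.2 all name an increase. The DAIDS grading table (Protocol Appendix 9) agrees: its LDL entry is "LDL, Fasting, High", total cholesterol is likewise graded only when high, and there is no grade for a low value of either.

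**Step 2: count of the SAP list by direction** (Appendix 8, Cholesterol increase, both pages of the table).

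| Group | Terms | Number |
|---|---|---|
| Fall in a cholesterol-carrying fraction other than HDL | LDL, IDL, VLDL and non-HDL cholesterol decreased | 4 |
| Fall in a ratio | LDL/HDL and total cholesterol/HDL decreased | 2 |
| Low HDL | HDL decreased; hypo-HDL-cholesterolaemia | 2 |
| Direction not stated (abnormal) | seven terms | 7 |
| All remaining terms | increases, hyperlipidaemias and general lipid disorders | 18 |
| Total | | 33 |

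Shares: 4/33 = 12%; (4 + 2)/33 = 18%; (4 + 2 + 2)/33 = 24%.

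The four fraction terms contradict the label outright. The two ratio terms do not denote an increase, but a ratio can fall because its denominator, HDL, rises. They therefore need not mean that LDL or total cholesterol fell. The two low-HDL terms can be defended as dyslipidaemia, though not as a cholesterol increase.

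**Step 3: what has to happen for a participant to be miscounted.** SAP Section 5.6.2 counts participants with at least one treatment-emergent adverse event. Protocol Appendix 9 notes that a laboratory abnormality is not necessarily an adverse event. So three conditions must hold:

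1. The fall is reported as a treatment-emergent adverse event.
2. It is coded to one of these terms.
3. The participant has no other listed term, since otherwise he or she is already in the count.

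**Step 4: size.** The planned number is about 50 participants. One participant who meets all three conditions adds 1/50 = 2 percentage points to the overall incidence. As an illustration on an assumed count, two true cases give 2/50 = 4%, and one miscounted participant makes it 3/50 = 6%. The SAP also allows some safety analyses by JNJ-6379 group (Sections 5.1.10 and 5.6). The documents do not give the group sizes. For an assumed 10 to 30 participants per group, the step is 1/30 = 3.3 to 1/10 = 10 points. With no such participant, the incidence is unchanged.

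**Step 5: list length after the change.** 33 − 6 = 27 terms if the low-HDL terms stay; 33 − 8 = 25 if they go.

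**The case against.** The strongest case against acting is that direction remains visible elsewhere and that nothing depends on this count. Laboratory cholesterol is analysed with low/normal/high shift tables and worst grade by direction (SAP Section 5.6.3.1), and grading is for high values only. Each adverse event is also summarised under its own term, so a decreased event could be identified. Safety summaries are descriptive and no formal test is planned. No document reports a single lipid-decrease adverse event. All of this stands and keeps the point minor. It does not correct the AESI incidence, which is computed from the list as written.

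The protocol's phrase about related events is slightly wider than increase alone. It cannot reasonably be stretched to cover a fall in LDL, IDL, VLDL or non-HDL cholesterol.

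Four stronger readings are tempting, and the documents do not support them:

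- A reader might infer that any participant whose LDL falls is tabulated as a cholesterol-increase case. Only a reported and coded treatment-emergent adverse event counts.
- A reader might infer that every misdirected report adds 2 points. The summary counts participants, so a report in someone already counted adds nothing.
- A reader might take all six terms (18%) as plain opposites. Only the four fraction terms are; a ratio can also fall because HDL rises.
- A reader might note that the other SMQ sources in Appendix 8 are marked (Modified) and this one is not, and conclude that the list was left untrimmed by oversight. The SAP does not say what that mark means, and the SMQ itself is not available to check.

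**Conclusion.** The mismatch is real and small. The list that defines Cholesterol increase contains four terms (12% of 33) that denote the opposite change, and two ratio terms that do not denote an increase. As written, the rule would count a participant with a treatment-emergent adverse event coded only to one of these terms as a cholesterol-increase case.

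The effect is 2 percentage points per such participant if 50 are analysed, more within a JNJ-6379 group of unstated size, and zero if no such event is reported. The conclusion rests on the protocol's own direction for the event and on SAP Section 5.6.2 making Appendix 8 the definition. It does not depend on why the terms are there. Because the safety summaries are descriptive, this is a desirable correction and not an essential one.

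**What to change.** In SAP Appendix 8, under Cholesterol increase:

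- Remove the four fraction terms (LDL, IDL, VLDL and non-HDL cholesterol decreased) and the two ratio terms (LDL/HDL and total cholesterol/HDL decreased).
- State whether the two low-HDL terms are kept as dyslipidaemia or removed as well, so that the list follows a stated principle.

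If the full list is intended, keep it but rename the category, for example Lipid abnormality, and show increases on a separate line. That resolves the mismatch equally well.

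Either route is a text edit to the term list, with the matching change to the AESI table. It needs no new data and no change to study conduct.

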6.9. Appendix 10 Laboratory Toxicity Grading

The laboratory abnormalities will be determined according to the criteria specified in the DAIDS Toxicity Grading Scale (see Clinical Protocol Appendix 9, DAIDS Table) or in accordance with the normal ranges of the clinical laboratory if no gradings are available.

